8.4 Analysis Methods

8.4.1 Methods of Analysis

All statistical procedures and non-compartmental analyses (NCA) will be completed using SAS® version 9.4 or higher or WinNonlin v8.1, respectively, or more recent versions of either program.

The placebo arms will be combined for all descriptive summaries of subject disposition, demography and Baseline characteristics, PD, VOCs, and safety.

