3.2 Treatment Assignment/Randomization

Subjects who meet the eligibility criteria and have given written informed consent will be randomized in a 2:2:1:2:2:1 allocation to one of 6 treatment groups. Approximately 12 subjects will be randomized to each active rifaximin treatment and approximately 6 subjects to each placebo group. The treatment groups will be run in parallel.

- Group 1: 40 mg rifaximin ER, BID
- Group 2: 40 mg rifaximin DER, BID
- Group 3: Placebo for 40 mg rifaximin, BID

- Group 4: 80 mg rifaximin ER, BID
- Group 5: 80 mg rifaximin DER, BID
- Group 6: Placebo for 80 mg rifaximin, BID

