3.3 Procedures for Breaking the Blind

Subjects, study staff, and the Sponsor will be aware of the dose groups (2 x 20 mg capsules BID or 4 x 20 mg capsules BID) but will be blinded to active or placebo. Only in the case of an emergency, when knowledge of the study drug is essential for the clinical management or welfare of the subject, will the Investigator be allowed to unblind a subject's treatment assignment. To discuss breaking of the blind, the Investigator should contact the Medical Monitor. The Investigator will unblind via an Interactive Response Technology system.

If the Investigator breaks the blind for an individual subject, the reason must be in the subject's source documents and the subject will be removed from the study.

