8.4.6 Analysis of Safety

All adverse events occurring during the study will be recorded and classified based on MedDRA terminology. Only adverse events that occur after the start of study drug, (treatment emergent adverse events [TEAEs]); all AEs will be included in by-subject listings.

TEAEs will be summarized for the entire population, by dose within formulation and combined placebo, and by severity and relationship to study medication. Each subject will be counted only once within a system organ class or a preferred term by using the adverse event with the highest severity or greatest relationship, respectively, within each category.

Treatment-emergent AEs will be summarized as follows:

- Number and percentage of subjects experiencing TEAEs,
- Number and percentage of TEAEs by relationship to study treatment (i.e., related or unrelated),
- Number and percentage of TEAEs by severity,
- Number and percentage of subjects experiencing serious AEs (SAEs),
- Number and percentage of subjects experiencing study drug-related SAEs,
- TEAE leading to permanent treatment discontinuation,
- TEAEs with an outcome of death.

All SAEs, AEs leading to premature withdrawal from the study, and all deaths, will be listed.

Reports of diarrhea due to *C. difficile* will be summarized.

Vital signs will include supine blood pressure (mmHg), heart rate (beats per minute), body temperature, and O₂ saturation. Vital signs will be summarized at Baseline and for each day when vital signs were obtained. Changes from Baseline in vital sign measurements will also be summarized. For each summary the N, mean, median, SD, minimum, and maximum values will be given for all subjects, by dose within formulation and combined placebo. Pretreatment vital signs obtained closest in time to first dose of study drug will be used for summarization and analysis of Baseline and change from Baseline vital signs.

Changes from Baseline in abbreviated physical exam findings of clinical significance will be summarized and listed.

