8.4.7 Clinical Safety Laboratory Findings

Clinical safety laboratory data (hematology, chemistry, and urinalysis) will be summarized at Baseline and at each visit per the schedule of assessments, as well as changes from Baseline in laboratory parameters. For each summary the N, mean, median, SD, minimum, and maximum values will be given by dose within formulation and combined placebo. Pretreatment laboratory values obtained closest in time to first dose of study drug will be used for summarization of Baseline and change from Baseline. Pregnancy testing results (urine and serum) will be presented in by-subject listings.

Clinical safety laboratory tests performed during the study will be primarily analyzed by a central clinical laboratory.

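### Dose level is open but the two capsule-count placebo arms appear only as one combined column, so half of each dose's placebo comparator for reported or judged events is not capsule-matched

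*Combined protocol and SAP*

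**What the plan says.** Section 3.2 randomises about 60 subjects 2:2:1:2:2:1 to six parallel groups. There is one placebo arm per dose level: Group 3 matches the 40 mg arms, and the other is "Group 6: Placebo for 80 mg rifaximin, BID". Table 1 in Section 5.3 gives Group 3 four capsules a day and Group 6 eight, with 6 subjects each.

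Section 3.3 limits the blind. "Subjects, study staff, and the Sponsor will be aware of the dose groups", it says, "but will be blinded to active or placebo".

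Section 8.4.1, repeated in the synopsis, then pools the placebo arms: "The placebo arms will be combined for all descriptive summaries of subject disposition, demography and Baseline characteristics, PD, VOCs, and safety". The safety sections follow this layout. Section 8.4.6 has: "TEAEs will be summarized for the entire population, by dose within formulation and combined placebo". Section 8.4.7 does the same for laboratory data: "values will be given by dose within formulation and combined placebo". No planned summary shows Groups 3 and 6 apart, and no reason for pooling is given. By-subject AE listings are planned. In the synopsis, VOC and opioid summaries are optional.

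**The concern.** With the capsule count known to everyone, the double-blind comparison exists only within a capsule count: Groups 1 and 2 against Group 3, and Groups 4 and 5 against Group 6. The design provides both placebo arms, but the tables do not show them.

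This matters for outcomes shaped by what subjects report or investigators judge while knowing the dose level. Those are TEAEs, their severity and relatedness (a binary investigator judgement in Section 7.7), and VOCs, which require a facility visit and analgesia. Opioid use, which subjects report themselves, is in the same position. Knowing one is on the higher dose, or simply swallowing more capsules, could change reporting with or without active drug. Biomarkers measured in a laboratory are much less exposed.

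Safety and tolerability is one of the two objectives, and the safety tables are laid out by dose. A reader comparing a dose column with the placebo column could take a reporting difference for a drug effect and would have no summary with which to check it.

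**Working it through.** **Plan's own figures.** 60 × 2/10 = 12 per active arm and 60 × 1/10 = 6 per placebo arm; 4 × 12 + 2 × 6 = 60, as stated. The plan gives no alpha, power, event rate or effect size. Event rates and d below are therefore assumptions.

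**Make-up of the comparator.** Combined placebo has 12 subjects. For either dose, 6 of 12 (50%) have the same capsule count and 6 of 12 do not.

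**Shift from pooling.** Let the reported event rate be p in the 2-capsule groups and p + d in the 4-capsule groups, on active and placebo alike, with no drug effect.
- Combined placebo: (6p + 6(p + d))/12 = p + d/2.
- 80 mg minus combined placebo: +d/2. 40 mg minus combined placebo: −d/2.
- Each dose minus its own placebo: 0.
- 80 mg minus 40 mg: d, however placebo is tabulated, because a shared control cancels.
- All active minus all placebo: 0, because the ratio is 24:6 at both levels.

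| Assumed d | Shift per dose versus combined placebo | 80 mg minus 40 mg (not caused by pooling) |
|---|---|---|
| 10 points | ±5 | 10 |
| 15 points | ±7.5 | 15 |
| 20 points | ±10 | 20 |

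Example with p = 30% and d = 20 points: the 40 mg arms and Group 3 show 30%, the 80 mg arms and Group 6 show 50%, and combined placebo shows 40%. The 80 mg arms look 10 points worse than placebo and the 40 mg arms 10 points better. Separate columns would show 50% against 50% and 30% against 30%. A negative d reverses the signs.

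**Precision given up by using only the matched arm.** SE = √(p(1−p)(1/n1 + 1/n2)).
- 12 v 6 against 12 v 12: ratio √(0.2500/0.1667) = 1.22. At p = 30% the SE goes from 0.187 to 0.229.
- 24 v 6 against 24 v 12 (ER and DER merged): ratio √(0.2083/0.1250) = 1.29. At p = 30% it goes from 0.162 to 0.209.

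**Bias against variance.** Pooling adds squared bias d²/4 and saves variance p(1−p)(1/6 − 1/12) = p(1−p)/12. With one p used for the variance, the matched contrast has the lower mean squared error only if d exceeds 2√(p(1−p)/12) in absolute value.

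| Assumed p | Break-even d |
|---|---|
| 10% | 0.17 |
| 20% | 0.23 |
| 30% | 0.26 |
| 50% | 0.29 |

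**Placebo-subtracted dose difference.** Subtracting each level's own placebo from 80 minus 40 mg changes the variance factor from 1/24 + 1/24 = 0.0833 to 0.0833 + 1/6 + 1/6 = 0.4167. The SE is √(0.4167/0.0833) = 2.24 times larger; at p = 30% it goes from 0.13 to 0.30. Per formulation the factor goes from 0.1667 to 0.5000, a ratio of 1.73.

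**The case against.** The strongest reply is that pooling two arms of 6 is a sound choice in a descriptive study of 60 with no formal sizing. The documents give no evidence that d differs from zero. At event rates of 30% or 50%, pooling has the lower mean squared error across the whole assumed range of 10 to 20 points. All 12 placebo subjects come from the same concurrent randomisation, so baseline comparability is intact. No between-arm harm test is planned, and the listings would let someone rebuild the split. All of this stands. It defeats any rule that by-dose results be read only against the 6 matched placebo subjects, or that dose differences be placebo-subtracted.

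It does not defeat showing the two arms beside the combined column, which costs no precision. Randomisation does not protect reporting that happens afterwards by people who know the dose. Listings are not a summary. With no model or test, the columns themselves are what readers interpret.

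Two stronger readings are tempting. A reader might infer that the by-dose comparisons lose their blinded control altogether. They do not: half the combined column is capsule-matched and blinded, so the match is diluted. A reader might also infer that pooling creates a false 80 versus 40 mg gradient. It does not: any such gradient comes from the open dose level in Section 3.3 and is the same under any placebo layout.

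**Conclusion.** The point holds as a minor one about presentation. Every planned safety summary, and any VOC summary, shows placebo only in combined form, so half of each dose's placebo comparator is not capsule-matched and had a known, different dose level. A non-drug difference d between capsule groups shifts each dose-versus-combined-placebo difference by d/2, upward for one dose and downward for the other: 5 to 10 points for an assumed d of 10 to 20.

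This assumes that d is additive and equal on active and placebo. Its size and sign are not in the documents, and it could be zero, so a claim that harm will be overstated at 80 mg and understated at 40 mg is not supported. The overall rifaximin-versus-placebo contrast is unaffected. What the plan loses is the placebo evidence by capsule count that would help a reader judge whether an 80 versus 40 mg difference in reported events reflects drug or reporting.

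**What to change.** In Sections 8.4.1 and 8.4.6 and in the synopsis:
- Keep the combined placebo column.
- Add Group 3 and Group 6 as separate supplementary columns for TEAEs (including severity and relationship), for AE-related discontinuation, and for VOCs and opioid use if these are summarised.
- State that comparisons of reported events between dose levels are not blinded.

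Do not require by-dose contrasts to be read only against the matched placebo, and do not require placebo-subtracted dose differences.

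The cost is wording and two table columns. The assignments exist from randomisation and no new data are needed. Section 8.0 leaves detailed methods to an SAP finalised before database lock, so the change can be prespecified there. The downside is imprecision. With about 6 subjects per column, an event with a true rate of 10% appears at least once with probability 1 − 0.9^6 = 47%, against 1 − 0.9^12 = 72% in the combined column. The new columns should be labelled descriptive only.

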8.4.2 Subject Disposition

Subject disposition will be summarized for all randomized subjects, by dose (40 mg BID or 80 mg BID) within formulation (ER or DER), and combined placebo and will include the number of subjects randomized; number and percentage of subjects who completed or prematurely discontinued the study, classified by reasons for premature discontinuation; the number of subjects randomized at each study site; and the number and percentage of subjects who completed or discontinued the study at each study site.

8.4.3 Demographics and Baseline Characteristics

Age, gender, race, ethnicity, height, and weight will be summarized for the entire population, by dose within formulation and combined placebo. Baseline characteristics will include number of VOCs in the previous year, concurrent treatment with HU, use of IOA and orally administered opioids (in morphine milligram equivalents [MME]), and SCD genotype.

8.4.4 Pharmacokinetics

Concentrations of rifaximin and its metabolite (25-desacetyl rifaximin) will be summarized by formulation and by dose. Concentrations will be summarized for samples taken for 8 and 72 hours after the initial dose and the final dose, respectively.

Dense sampling for initial dose (first dose interval): C_{max} , T_{max} , AUC_{last} , AUC_{0-8h} , and MR_AUC_{0-8h} , will be summarized.

Dense sampling for final dose: C_{max} , T_{max} , C_{min} , C_{avg} , AUC_{0-8h} , CL/Fss , Vz/Fss , R_{Cmax} , $R_{AUC\tau}$, AUC_{last} , AUC_{inf} , λz , $t_{1/2}$, and MR_AUC_{0-8h} , will be summarized.

Steady state levels will be summarized for all subjects based on C_{trough} on Day 8, Day 15, and Day 29.

Additional PK parameters maybe calculated if it deemed necessary.

LIST OF PHARMACOKINETIC TERMS

Parameter	Definition
AUC_{last}	Area under the plasma drug concentration-time curve from time 0 to the last quantifiable drug concentration
AUC_{inf}	Area under the plasma drug concentration-time curve from time 0 extrapolated to infinity

AUC _{0-8h}	Area under the plasma drug concentration-time curve from time 0 through 8 hours
C _{avg}	Average plasma concentration at steady-state
C _{max}	Maximum observed plasma concentration
C _{min}	Minimum observed plasma concentration
C _{trough}	Observed plasma concentration at the end of a dosing interval, just prior to the administration of the next dose
T _{max}	Time of maximum observed plasma concentration
t _{1/2}	Apparent terminal elimination half-life
λ _z	Terminal elimination rate constant
CL/F _{ss}	Apparent systemic extravascular clearance at steady-state
V _z /F _{ss}	Apparent extravascular volume of distribution during the terminal elimination phase at steady-state
R _{AUC}	Accumulation ratio of AUC _r at steady-state to AUC _{last} after the first dose
R _{Cmax}	Accumulation ratio of C _{max} at steady-state to C _{max} after the first dose
MR AUC	Metabolite-to-parent ratio for AUC

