	
the study site for 8 hours after dosing and safety parameters and samples for PK (rifaximin and 25-desacetyl rifaximin) will be collected for 8 hours post-dose. After completing all 8-hour assessments, and the safety parameters are acceptable to the Investigator, the subjects can go home. Subjects will administer their Day 1 PM dose at home.
 
Subjects will return to the study site for outpatient visits on Days 8, 15, and 29 (± 1 day each) for pre-dose PK, PD, and safety assessments.
 
At the final visit (Day 29 [± 1 day]), subjects will administer only the AM dose of treatment. Subjects will remain at the clinical site through 8 hours post-dose for collection of PK samples. Subjects will return to the site on the following days for post-final dose PK assessments as follows:
 
Day 30:
 
 • 24 hours post-dose • 30-hours post-dose 
Day 31: 48 hours post-dose
 
Day 32: 72 hours post- dose
 
Two weeks after the last dose subjects will return to the study site for a final follow-up visit on Day 43 (± 3 days). Subjects will be discharged from the study after completing all assessments on the Day 43 visit.
 
At every study visit, subjects will also report opioid use since their previous visit. Site staff will record opioid use.
 
Safety, tolerability, PK, and PD data will be collected during each visit at the timepoints listed in the Schedule of Assessments.

STUDY DURATION	Subject participation will be up to 9 weeks, including a Screening Period of up to 21-days, a 4-week Treatment Period, and 2-week Follow-up.
SUBJECT POPULATION	Male and non-pregnant, non-nursing females ≥ 18 and ≤ 70 years with SCD and at least 2 VOCs in the previous 12 months.
NUMBER OF SUBJECTS	Up to 60; 12 subjects in each of 4 active rifaximin groups and 6 subjects in each of 2 placebo groups.

NUMBER OF CENTERS	Approximately 20
LOCATION	Multicenter study in North America, Middle East, and Africa

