	
Blood samples for PK analysis will be collected at the following timepoints:
 
• Day 1: pre-dose, 0.5, 1, 1.5, 2, 3, 4, 5, and 8-hours post-dose• Day 8 and Day 15: pre-dose and 0.5, 1, and 2-hours post-dose.• Day 29: pre-dose, 0.5, 1, 1.5, 2, 3, 4, 5, and 8-hours post-final dose.• Day 30: 24 and 30 hours post-final dose• Day 31: 48 hours post-final dose• Day 32: 72 hours post-final dose• During medical facility visit for VOC with estimated time of last dose, when possible. 
PD biomarkers (absolute neutrophil count [ANC], circulating aged neutrophils [CANs], serum CD62L, high sensitivity C-reactive protein [hsCRP], the gut permeability biomarkers intestinal fatty-acid binding protein [iFABP], lipopolysaccharide [LPS], and the gut bacteria biomarker urine 3-indoxyl sulfate [3-IS Urine]) will be collected at the following timepoints:
 
• Day 1: pre-dose• Day 8, Day 15, and Day 29: during each visit – pre dose• Day 31• Day 43• During medical facility visit for VOC, when possible. 
Safety:
 
Safety will be assessed throughout the duration of the study by collection of adverse events (AEs), vital signs (systolic and diastolic blood pressure, heart rate, oral body temperature, and oxygen saturation), clinical safety laboratory tests (hematology, chemistry, urinalysis, and C-reactive protein), physical exams (PEs), and electrocardiograms (ECGs).
 
Exploratory Assessments:
 
At every study visit, subjects will report, and the site staff will record, opioid use since their previous visit.
 
Information on any potential VOCs experienced during the study will be collected as follows:

--	---

	
 • Dates and duration of each episode. A VOC is defined as: 
 ○ The occurrence of appropriate symptoms consistent with a painful crisis, acute chest syndrome (ACS), or priapism, and ○ Requires visit to a medical facility, and ○ Receipt of either a parenteral or oral opioid or NSAID analgesia. • Categorization of VOCs. Subcategories are uncomplicated pain crises, acute chest syndrome (ACS), hepatic sequestration, splenic sequestration, and priapism (requiring healthcare visit). • Intravenous opioid analgesia (IOA) and oral opioid use during VOCs, including date/time of each start and stop of treatment, dose, drug, inpatient/outpatient setting, and date/time of readiness-to-discharge.

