5.3 Dosing and Dosing Schedule

Each subject will be dispensed study drug at each visit with enough capsules to dose through their next visit.

During the Treatment Period, eligible subjects will take study drug BID according to their treatment assignment as outlined in [Table 1](#). Dosing will begin on Study Day 1 (Visit 2) and continue through Study Day 29 (Visit 5). Doses will be taken orally with water, and capsule will be swallowed whole. Study participants should be instructed to take the study drug on an empty stomach. The morning (AM) dose should be taken on an empty stomach, and subjects must avoid food for two hours after taking the study drug. The evening (PM) dose should be taken on an empty stomach (at least two hours after the last meal), and subjects must avoid food for two hours after taking the study drug.

On Days 1, 8, 15, and 29, participants will fast for a minimum of 10 hours prior to, and 2 hours after, the morning study drug administration. Water will be restricted from one hour prior to dosing through one hour following dosing, except for the water that will be consumed at dosing. Study drug should be administered with approximately 240 mL of water.

Table 1 Dosing by Treatment Assignment

Dose Group	Formulation	Study Day	Total Number of Capsules	Capsule (mg)	Daily Dose (mg)	No. of Subjects
1	ER	Daily	4 (2 in AM, 2 in PM)	20	80	12
2	DER	Daily	4 (2 in AM, 2 in PM)	20	80	12
3	Placebo	Daily	4 (2 in AM, 2 in PM)	20	-	6
4	ER	Daily	8 (4 in AM, 4 in PM)	20	160	12
5	DER	Daily	8 (4 in AM, 4 in PM)	20	160	12
6	Placebo	Daily	8 (4 in AM, 4 in PM)	20	-	6

Note: AM and PM refer to approximate 12-hour period between doses

Before any study drug is administered, each subject will be instructed by the Investigator or his/her representative on the proper self-administration of study drug. All unused study drug will be returned to the study site at the next clinic visit.

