6.2.1 Assessment of Pharmacokinetics

Blood samples for analysis of plasma rifaximin and 25-desacetyl rifaximin pharmacokinetics will be collected as described in [Appendix 2](#). Full PK assessments through 8-hour and 72-hours post dose will be performed at Visit 2 (Day 1) and Visits 5 to 8 (Days 29 to 32), respectively. Samples will be obtained pre-dose and at 0.5, 1, 1.5, 2, 3, 4, 5, and 8-hours post-dose on Days 1 and 29.

At Visit 3 (Day 8) and Visit 4 (Day 15) samples will be obtained pre-dose and at 0.5, 1, and 2-hours post-dose.

Additionally, post-final dose assessments will be done on:

Visit 6: 24 and 30 hours post-final dose

Visit 7: 48 hours post-final dose

Visit 8: 72 hours post-final dose.

The windows around the collection timepoints are:

- within 15 minutes prior to dose for pre-dose samples,
- ± 5 minutes for samples taken at 0.5 hours through 1.5 hours, and
- ± 10 minutes for samples taken 2 hours through 8 hours.
- ± 2 hours for samples taken 24 hours through 72 hours.

In addition, when possible, a sample will be obtained for PK assessment during a medical facility visit for a VOC. The time of the last dose of study drug will be recorded.

If the subject is to begin treatment with a P-gp inhibitor, a plasma sample for PK analysis should be collected during treatment with both rifaximin and the P-gp inhibitor. This sample should be collected at the next scheduled visit, if possible. Alternately, an unscheduled PK sampling visit

should occur. The date and time of the last 2 rifaximin doses, as well as the last 2 doses of the P-gp inhibitor should be recorded.

Study participants should be instructed to take the study drug on an empty stomach. The morning (AM) dose should be taken on an empty stomach, and subjects must avoid food for two hours after taking the study drug. The evening (PM) dose should be taken on an empty stomach (at least two hours after the last meal), and subjects must avoid food for two hours after taking the study drug.

On Days 1, 8, 15, and 29, Participants will fast for a minimum of 10 hours prior to, and 2 hours after, the morning study drug administration. Water will be restricted from one hour prior to dosing through one hour following dosing, except for the water that will be consumed at dosing.

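### The AUC accumulation ratio sets a steady-state AUC over the dosing interval (about 12 h) against a Day 1 AUC that stops at 8 h or earlier, so it overstates accumulation whenever exposure continues after the last Day 1 quantifiable sample

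*Combined protocol and SAP*

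**What the plan says.** Section 8.4.4 lists an accumulation ratio for AUC among the final-dose parameters. Its list of terms defines the ratio as "Accumulation ratio of AUC" (a subscript that the extracted table garbles) "at steady-state to AUC" (subscript last) after the first dose. The final-dose parameter list in the same section prints the ratio with subscript tau, which settles the reading.

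The denominator, AUC_last, is defined as "Area under the plasma drug concentration-time curve from time 0 to the last quantifiable drug concentration". It has no fixed end time.

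The two windows follow from other sections:

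- **Dosing interval.** The note to Table 1 in Section 5.3 says that "AM and PM refer to approximate 12-hour period between doses".
- **Day 1 sampling.** The synopsis gives "Day 1: pre-dose, 0.5, 1, 1.5, 2, 3, 4, 5, and 8-hours post-dose". Section 6.2.1 and Appendix 2 agree.
- **After 8 h on Day 1.** The subject goes home, and the synopsis says "Subjects will administer their Day 1 PM dose at home". No later Day 1 sample exists.

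Section 8.4.4 nevertheless heads the Day 1 list "Dense sampling for initial dose (first dose interval"), although the profile covers only the first 8 h of an interval of about 12 h. AUC0-8h is listed for both Day 1 and Day 29 but is not used in the ratio. Neither the synopsis nor Section 8.5.4 changes the definition.

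**The concern.** An accumulation ratio compares exposure over the same window after the first dose and at steady state. Here the numerator spans about 12 h and the denominator at most 8 h, so the ratio can exceed 1 with no accumulation at all. A concentration profile that is flat over 12 h and identical on both days would give 12/8 = 1.5.

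The inflation depends on how much exposure falls after the last quantifiable Day 1 sample, and so on release profile, lag, half-life and assay limit. Both products are controlled-release, and the delayed one (DER) targets the mid-GI tract (Section 1.2), so late exposure cannot be dismissed. The factor may differ between ER and DER or between dose levels, and could be read as a formulation or dose effect. Characterising PK is part of the first objective, and R_AUC is the only planned measure of AUC accumulation.

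**Working it through.** The documents state no value for R_AUC, so there is no figure to reproduce.

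**1. Direction, by algebra.** Let t be the last quantifiable Day 1 time, t ≤ 8 h, and take tau = 12 h.

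- Matched ratio: R12 = AUC0-12h(steady state) / AUC0-12h(Day 1)
- As written: Rw = AUC0-12h(steady state) / AUC0-t(Day 1)
- Hence Rw = R12 × F, with F = AUC0-12h(Day 1) / AUC0-t(Day 1) ≥ 1. F exceeds 1 whenever there is exposure between t and 12 h.

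**2. One case worked through.** Assume one compartment, linear PK, first-order input ka = 0.35/h, half-life 4 h (k = 0.1733/h), no lag, unit dose and volume.

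AUC0-T = ka/(ka − k) × [(1 − e^(−kT))/k − (1 − e^(−ka·T))/ka]

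- Day 1: AUC0-12h = 4.43 and AUC0-8h = 3.26
- Steady state: AUC0-12h = 1/k = 5.77. Summing the single-dose areas over 0-8, 12-20, 24-32 h and so on gives AUC0-8h = 4.40.
- True 12 h ratio: 5.77/4.43 = 1.30
- As written: 5.77/3.26 = 1.77
- 0-8 h ratio: 4.40/3.26 = 1.35

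With a 3 h lag the three ratios are 1.60, 2.96 and 1.94.

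**3. Assumed grid.** Inputs: first-order (1.0 or 0.35/h) or zero-order (6, 8 or 12 h); half-life 1, 2, 4 or 6 h; lag 0, 1, 2 or 3 h. That is 5 × 4 × 4 = 80 cases. True areas, 8 h sample quantifiable:

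| Input | F (inflation as written) | Excess of the 0-8 h ratio over the true 12 h ratio |
|---|---|---|
| First-order | 1.01 to 1.99 | 0 to 30% |
| Zero-order, 6-8 h | 1.06 to 2.79 | 0 to 72% |
| Zero-order, 12 h | 1.61 to 2.83 | 7 to 89% |

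The overall median of F is 1.60. In the 24 cases with a true ratio of at most 1.10, the ratio as written reaches 2.22 and is 1.25 or more in 12; the 0-8 h ratio never exceeds 1.20. Counts and median reflect equal weighting of assumed cases and are not probabilities for this trial.

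**4. Planned sample times.** With the linear-up log-down rule and the Day 29 pre-dose value used at 12 h, the inflation is 1.01 to 2.89. The 0-8 h ratio exceeds the true 12 h ratio by 0 to 92%.

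**5. Unquantifiable 8 h sample.** With an assay limit at 5, 10, 20 or 30% of Day 1 C_max, the Day 1 8 h sample is lost in 1, 3, 5 and 8 of the 80 cases, and t falls to 4 or 5 h. In these 17 case-limit pairs F is 1.09 to 2.02. Integrating both days to the same t leaves an error of 0 to 1%. Using 0-8 h on Day 29 over 0-t on Day 1 leaves 8 to 86%.

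**6. ER against DER.** At half-life 2 h, 1.0/h input gives F = 1.08 with no lag and 1.18 with a 2 h lag, but 8 h zero-order release with no lag gives 1.38. The direction of any formulation difference is not fixed.

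**7. Secondary: the numerator.** AUC_tau is not listed as a Day 29 parameter, and there is no sample between 8 and 24 h. Relative to its true value, the estimate is 0.87 to 1.00 with the pre-dose trough used at 12 h, 0.72 to 1.00 with log-linear interpolation from 8 to 24 h, and 0.93 to 1.34 with linear interpolation.

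**The case against.** The strongest objection is that only the denominator is explicit. Tau is undefined, the table subscript is damaged, and the only fixed-window AUC listed for Day 29 is AUC0-8h. If the numerator were programmed as 0-8 h, the mismatch would vanish for every subject with a quantifiable 8 h sample. Section 8.0 also leaves detailed methods to a later SAP. But nothing in the text states the 0-8 h reading: the parameter list prints tau, dosing is about every 12 h, and AUC0-8h has its own separate name. Even on that reading, subjects with t below 8 h would still be mismatched.

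The objection on size stands. No half-life, release duration or assay limit is given, and 48 of the 80 cases assume zero-order release over 6 to 12 h. First-order input alone has a median factor of 1.32, and first-order input without a lag gives 1.01 to 1.45. If exposure is nearly over by the last quantifiable Day 1 sample, the inflation is negligible.

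The objection on weight also stands. R_AUC is descriptive, steady state is judged from trough concentrations, the sample size does not rest on it (Section 8.2), and the planned PK/PD relations in Section 8.4.5 use other parameters. A reader could form the matched ratio from the planned AUC0-8h summaries.

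**Conclusion.** The concern holds. With tau read as the dosing interval of about 12 h, the definition compares unequal windows, and in true areas it can only overstate AUC accumulation. That much is algebra. The size rests wholly on assumptions: a factor of 1.01 to 2.83 over the grid when the 8 h sample is quantifiable. The consequence is confined to one descriptive parameter. It should still be corrected before database lock, because an analyst applying the stated definition would report accumulation that partly reflects the sampling window.

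**What to change.** In Section 8.4.4, redefine R_AUC as Day 29 AUC0-8h divided by Day 1 AUC0-8h and label it a 0-8 h accumulation ratio. Apply the same below-quantification rule on both days: if the 8 h sample is not quantifiable on either day, integrate both days to the same earlier time and flag the subject. State that with a lag or slow release this ratio can still exceed the 12 h ratio.

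In the SAP, define AUC_tau on Day 29 as 0-12 h and state how its 8-12 h part is obtained. C_avg and CL/Fss would normally rest on it, although the protocol gives no formula for either.

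The cost is wording only, since both AUC0-8h values are already planned. The fix is partial: in true areas up to 89% excess remains in the worst assumed case, against 183% as written. The new ratio was closer to the true 12 h ratio in all 80 cases, in true areas and from the planned sample times. A direct 12 h comparison would need an added 12 h sample on both days, taken before the evening dose on Day 1.
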